Proposed Research Protocol Form
Northwestern University Feinberg School of Medicine

Title: Association between bolus rate and the adequacy of labor analgesia using timed-intermittent boluses for maintenance of labor analgesia

Principal Investigator: [name].

Co-investigator (s): [name], MPH,

Affiliation: Department of Anesthesiology, Northwestern University Feinberg School of Medicine

1.0 Research Aims:

Aim 1: To evaluate the association between bolus rate and duration of adequate labor analgesia.

Hypothesis: Patients whose labor analgesia is maintained using timed intermittent boluses with a high-rate bolus (300 mL/h) will have a longer duration of adequate analgesia (time to first manual redose request) than patients whose timed bolus is delivered with a lower-rate bolus (100 mL/h).

2.0 Research significance:

Background:

Neuraxial labor analgesia is usually maintained by the intermittent or continuous injection of local anesthetic combined with opioid through a catheter sited in the lumbar epidural space. Pain from the first stage of labor is primarily due to lower uterine segment and cervical stretching. The pain signals enter the spinal cord through sensory nerves at the T10 through L1 dermatomes. Pain signals from the late first state and second stage of labor also arise from the vaginal and perineum. These signals travel with the pudendal nerve and enter the spinal cord at S2-S4. Thus, the anesthetic solution administered through the lumbar epidural catheter must spread cephalad in the epidural space to reach the T10 nerve roots and spinal cord, and must spread caudad to reach the caudal nerve roots in the epidural space.

Administration of anesthetic solution into the epidural space is usually accomplished by a combination of continuous infusion, provider-administered boluses and patient-administered boluses (patient controlled epidural analgesia [PCEA]). The optimal method for maintaining labor analgesia is unknown. Several studies have demonstrated that timed-intermittent boluses, in combination with patient-controlled epidural analgesia (PCEA), provide superior

maintenance of labor analgesia (less need and longer latency for provider intervention, lower local anesthetic consumption, less motor block) than maintenance with a continuous infusion with PCEA.¹⁻⁴ The mechanism for this difference is not known; however, one suggested mechanism is improved spread of the local anesthetic within the epidural space. Kaynar *et al.* injected methylene blue dye through a multi-orifice catheter using either a continuous infusion or intermittent bolus and the area of diffusion was measured on a piece of paper.⁵ The authors found that intermittent boluses were associated with a greater surface area of diffusion than continuous infusion. In a subsequent cadaver study, dye was injected into the lumbar epidural space, and cryomicrotome sections were taken.⁶ Dye flowed in rivulets through small channels in the epidural space, as opposed to moving as a unified front. The authors found dye injected at high pressures had more uniform spread through the epidural space, supporting the concept of intermittent epidural injection providing superior analgesia.

Epidural infusion pumps capable of delivering timed boluses of local anesthetic with PCEA recently became commercially available. Several infusion rates are available for delivering the timed bolus, and the optimal bolus rate is unknown. We hypothesize that patients whose labor analgesia is maintained using timed intermittent boluses with a high-rate bolus (300 mL/h) will have a longer duration of adequate analgesia (time to first manual redose request) than patients whose timed bolus is delivered with a lower-rate bolus (100 mL/h).

- .1 **Significance:** The findings from this study will help us better understand whether there is an association between bolus rate and adequacy of labor analgesia. This is important for guiding future clinical practice.

3.0 Investigational Plan

.1 Study design:

Randomized controlled double-blinded study

.2 Methods:

Size of study groups(s):

The primary outcome is the proportion of subjects in each group that have breakthrough pain requiring a manual bolus (redose) by the anesthesiologist. In previous studies that have used timed-intermittent boluses for maintenance of

labor analgesia, the percentage of patients that have required supplemental manual boluses of local anesthetic has ranged between 30-50%. We hypothesize that patients randomized to the rate of 300 mL/h will be less likely to require a supplemental manual bolus than those in the 100 mL/h group.^{1,7} Assuming that 50% of the patients in the 100 mL/h group will require supplemental manual boluses and 30% of patients in the 300 mL/hr group will required supplemental manual boluses, using a power of 0.8, and an alpha of 0.05Due to the dynamic nature of the labor and delivery floor in patients' clinical course and resultant decisions regarding their choices on pain control during labor there is a greater degree of unpredictability of enrolled patients being excluded from this study for both clinical and personal reasons. As a result 300 patients meeting inclusion criteria will be recruited to account for dropout and still maintain the ability to recruit the estimated 106 patients per study group.

Secondary outcomes are the total number of requested and delivered PCEA boluses, and bupivacaine consumption per hour of labor analgesia.

.2.1 Participant entry, exclusion and dropout criteria:

Inclusion criteria:

Nulliparous parturients who presents to the labor and delivery unit for an induction of labor or who are in spontaneous labor, and request neuraxial labor analgesia at < or = to 5cm cervical dilation are eligible to participate.

Exclusion criteria:

Patients who are not eligible to receive a combined spinal epidural (CSE) technique with 25 mcg of intrathecal fentanyl, non-English speaking, who experience failed CSE analgesia, need to have the epidural catheter replaced during labor, or who deliver within 90 minutes of initiation of labor analgesia will be excluded from the study.

.2.2 Protocol specific methods:

Parturients who meet the inclusion criteria will be approached by one of the investigators, or one of the anesthesiology research nurses, for study participation. Parturients who are willing to participate in the study will provide written consent. Patient demographics will be collected at study enrollment.

Cervical dilation will be confirmed by a member of the obstetric team prior to epidural catheter placement as is routinely done at our institution. A baseline pain visual analog scale (VAS) score will be obtained using a 100-mm unmarked line with the end points labeled "no pain" and "worst pain imaginable."

Labor analgesia will be initiated using CSE analgesia with 25 mcg of intrathecal fentanyl. An epidural test dose will be performed as routine (1.5% lidocaine with epinephrine 1:200, 3 mL).

Labor analgesia will be maintained using timed-intermittent boluses of local anesthetic with PCEA using the CADD-Solis pump (Smiths Medical). An unblinded anesthesia research nurse will program the epidural pump and initiate the maintenance of labor analgesia.

The maintenance epidural solution for both groups will be bupivacaine 0.625 mg/mL with fentanyl 1.95 mcg/mL. The intermittent bolus volume will be 10 mL administered every 60 minutes. The first bolus will be given 30 minutes after intrathecal injection, as has been done in previous studies at our institution.⁷ The bolus rate will be 300 mL/h (2 minute 10 ml bolus infusion) in the high-rate bolus group, and 100 mL/h (6 minute 10 ml bolus infusion). In addition to the programmed boluses patients will be able to administer patient-controlled epidural analgesia (PCEA) boluses of 5 mL every 10 minutes to a maximum of 15 mL (three PCEA boluses in a one hour period).

The patient, anesthesiologist, and research nurse recording clinical data will be blinded to group assignment.

Fifteen minutes following the intrathecal dose, a VAS score and a sensory level of analgesia will be obtained. The following information will be obtained hourly until complete cervical dilation (10 cm): VAS pain score, sensory level, a modified Bromage score (0 - no motor paralysis; 1 - inability to raise extended leg, but able to move knee and foot; 2 - inability to raise extended leg and to move knee, but able to move foot; 3 - inability to raise extended leg or to move knee and foot).

The time to the first request for supplemental analgesia will be recorded on the study data sheet. The time, type and volume of local anesthetic used, and VAS scores before and 15 minutes after the redose will be recorded.

All other clinical management will be as per routine, and study participation will not interfere with anesthetic or obstetric care. Anesthesiologists will manage breakthrough pain in the usual manner (assessment of stage of labor and extend/density of neuraxial blockade, followed by the appropriate maneuver to reestablish adequate analgesia).

Following delivery, the patient will be asked to give one final VAS score and her overall satisfaction with labor using a 100 mm unmarked line (the left end labeled "not satisfied at all" and the right end labeled "extremely satisfied"). Mode of delivery, as well as the duration of the 1st and 2nd stage of labor will be recorded by study personnel.

Patient Controlled Epidural Analgesia (PCEA) pump utilization data will be downloaded from epidural pumps after delivery. This will include the time to first PCEA request, the number of PCEA demands, the number of times that PCEA boluses were delivered, the total amount of local anesthetic consumed.

4.0 Risks/Benefits:

Risks:

There is no risk of physical harm in this study. The study will not result in any change in management of the patient's pain other than the infusion rate of the timed-bolus epidural bolus, nor in any delay in diagnosis and treatment of pain.

Participants are at risk for loss of confidentiality. Strict measures will be in place to ensure that no loss of confidentiality occurs. All participants will be assigned a participant study number that will be used to identify them. One document will link the participant name to their participant number, and this will be kept in a password-protected computer in a locked office in the Prentice Women's Hospital. Only study investigators will have access to the study data.

Benefits:

Participants will derive no specific benefit from participation in this study; however, participation in this study will help us better understand the optimal rate for delivery of bolus doses of local anesthetic during maintenance of labor analgesia using timed-boluses.

Confidentiality:

The subjects' identity will be guarded by assigning a numerical code which is only known by the principal investigator. Data is stored in a department computer which is password protected. Each study subject will be assigned a study code number. The code will be used to link study data to patient identification (name) in a separate database. Subject data will be stored on secured computers at Northwestern University. Data access will be password protected and only available to study investigators. The data forms will be de-identified after the chart review prior to analysis. 5 years after manuscript the data both electronic and paper will be destroyed using the current departmental standards.

5.0 Data Analysis:

- .1 Data collection form:** Data collection forms will include all of the information outlined above in study methods.

.2 **Data evaluation:** The primary outcome will be the proportion of patients requiring supplemental manual boluses of local anesthetic. Secondary outcomes are the total number of requested and delivered PCEA boluses, and bupivacaine consumption per hour of labor analgesia. In addition, time to first PCEA request, time to first supplemental manual bolus, and motor block at 10 cm cervical dilation will be evaluated. Categorical data between groups will be compared using a chi-squared or Fisher's exact test, and continuous data will be compared using a two-tailed t-test or Mann Whitney U test as appropriate. Time outcomes will be compared between groups using a Kaplan–Meier survival analysis technique with log rank test. Patients undergo a cesarean delivery or do not request supplemental analgesia will be censored at the time of delivery. Labor pain will be calculated using the area under the VAS-time curve using the trapezium rule.

1.0 Labor Requirements: All labor will be performed by study investigators and the anesthesiology research nurses.

2.0 Consent: Please see attached consent form for this study.

.1 **Additional information for preparation of an IRB Submission:** N/A

References:

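### The sole aim is about time to first redose request, but the primary outcome is the proportion needing a manual bolus; the time analysis that matches the aim is unranked and has a faulty censoring rule

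*Combined protocol and SAP*

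**What the plan says.** **Aim and hypothesis.** Section 1.0 has one aim: "To evaluate the association between bolus rate and duration of adequate labor analgesia". Its hypothesis is that the 300 mL/h group "will have a longer duration of adequate analgesia (time to first manual redose request") than the 100 mL/h group. The Background in section 2.0 repeats this.

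**Primary outcome.** Section 3.0, Size of study groups, says: "The primary outcome is the proportion of subjects in each group that have breakthrough pain requiring a manual bolus (redose) by the anesthesiologist". Section 5.0, Data evaluation, agrees: "The primary outcome will be the proportion of patients requiring supplemental manual boluses of local anesthetic". Section 3.0 adds a hypothesis that fits this outcome, with the 100 mL/h group as comparator: "We hypothesize that patients randomized to the rate of 300 mL/h will be less likely to require a supplemental manual bolus". The sample size (50% against 30%, power 0.8, alpha 0.05, 106 per group) is for this comparison.

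**Secondary outcomes.** Sections 3.0 and 5.0 give the same list: "Secondary outcomes are the total number of requested and delivered PCEA boluses, and bupivacaine consumption per hour of labor analgesia".

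**Time analysis.** Section 5.0 then adds three further items, one of them time to first supplemental manual bolus. Time outcomes are compared by Kaplan-Meier and log-rank. Women who have a cesarean, or who make no request for supplemental analgesia, are censored at delivery.

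**Data and practice.** Section 3.0, Protocol specific methods: "The time to the first request for supplemental analgesia will be recorded on the study data sheet". The time of the redose is recorded too. The anesthesiologist handles breakthrough pain by assessment, "followed by the appropriate maneuver to reestablish adequate analgesia".

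**The concern.** There are two linked problems.

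First, the plan carries two hypotheses on two endpoints. A proportion says how many women needed a manual bolus, not how long analgesia lasted before one was needed. The confirmatory result therefore does not answer the sole aim as worded, and the analysis that does answer it stands outside the named outcomes. If the two results differ, the plan does not say which supports a statement about duration.

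Second, the event changes between sections. The aim, its hypothesis and the first time on the data sheet use the request. The section 5.0 endpoint is the bolus. The censoring rule goes back to the request and adds cesarean delivery without limiting it to women who have not yet been redosed. At stake is who counts as an event in the only analysis that addresses duration.

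**Working it through.** **1. The plan's own sample size.** Inputs from section 3.0: p1 = 0.50, p2 = 0.30, power 0.8, alpha 0.05. Two-sided testing and equal allocation are assumed, since neither is stated for this calculation.

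- Uncorrected: n = [1.96·√(2·0.4·0.6) + 0.842·√(0.5·0.5 + 0.3·0.7)]² / 0.20² = 93 per arm.
- Continuity-corrected: (93/4)·[1 + √(1 + 4/(93·0.20))]² = 103 per arm.

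The stated 106 is within 3% of 103, so the calculation is for the proportion. At 106 per arm, exact binomial enumeration gives:

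| Test | Power, 50% v 30% | Level, 40% in both arms | Level, 50% in both arms |
|---|---|---|---|
| Chi-squared | 0.850 | 5.0% | 4.6% |
| Fisher | 0.816 | 3.6% | 3.3% |

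The primary test is sound.

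**2. The time analysis with events counted properly.** The documents give no hazard ratio or durations. Carry over 50% and 30% as cumulative event rates, with proportional hazards and equal follow-up:

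- Hazard ratio = ln(0.7)/ln(0.5) = 0.515.
- Expected events = 106·0.5 + 106·0.3 = 84.8. Needed for 80% power: 72 (Schoenfeld) or 77 (Freedman).
- Power = Φ(√84.8/2 · |ln 0.515| − 1.96) = Φ(3.06 − 1.96) = 0.86.

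**3. The censoring sentence applied literally.** A woman redosed and later delivered by cesarean falls under the cesarean clause and is censored at delivery, so her event is lost. Let c be the cesarean share, assumed equal in both arms and unrelated to redosing. Event rates become 0.5(1 − c) and 0.3(1 − c).

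| c (assumed) | Events lost | Events left | Hazard ratio | Power |
|---|---|---|---|---|
| 10% | 84.8·0.1 = 8.5 | 76.3 | ln(0.73)/ln(0.55) = 0.526 | Φ(2.80 − 1.96) = 0.80 |
| 30% | 84.8·0.3 = 25.4 | 59.4 | ln(0.79)/ln(0.65) = 0.547 | Φ(2.32 − 1.96) = 0.64 |

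Simulation agrees. With labour analgesia assumed to average 8 h (lognormal, coefficient of variation 0.4) and a constant redose hazard, log-rank power falls from about 0.88 to 0.81 at c = 10% and to 0.65–0.67 at c = 30%. The primary proportion is unaffected, because the sentence does not apply to it.

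**4. Every kind of woman under the section 5.0 rule.**

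| Request | Manual bolus | Delivery | Status as written |
|---|---|---|---|
| No | No | Either | Censored at delivery |
| Yes | Yes | Vaginal | Event |
| Yes | Yes | Cesarean | Event by the endpoint, censored by the rule |
| Yes | No | Cesarean | Censored at delivery |
| Yes | No | Vaginal | Neither event nor censored |

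The last row can occur because the response to breakthrough pain is left to the anesthesiologist's judgment. Women whose catheter is replaced are excluded and do not fall in it. The documents do not say how often it would occur.

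**The case against.** The best defence is that the confirmatory plan is not ambiguous. Sections 3.0 and 5.0 name the same primary outcome, with its own directional hypothesis and a matching sample size. The title and the Significance paragraph speak of adequacy of analgesia, which the proportion fits. The time analysis is prespecified with a method, and its place after the primary and secondary outcomes implies a lower status. All of this stands. What it leaves is a sole aim that names duration, and a duration analysis outside the outcome list.

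A reader might infer that the trial is underpowered for its aim, or that two tests inflate the false-positive rate. The documents support neither. If the planning rates hold under proportional hazards, expected events exceed those needed. Error inflation would require claiming success on whichever test came out significant, which would breach the named primary.

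On the event, request and redose may have been meant as near-synonyms, and an analyst would probably censor women without a bolus at delivery and keep a redose that came before a cesarean. That is the sensible default, but it is not what the sentence says. A reader might also take the request/bolus difference as a known loss of power. It is not: the frequency is unknown, and the direction of any effect depends on how women with a request but no bolus are assumed to divide between the arms.

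**Conclusion.** The point holds as a mismatch between aim and primary outcome, together with a defective event and censoring rule in the time analysis. The mismatch and the wording of the rule rest on the text alone. Their effect is on interpretation: the named primary test can support a claim about how many women need a manual bolus, but not by itself a claim about how long analgesia lasts.

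The censoring effect is conditional. About 8 to 25 of roughly 85 events are lost if the sentence is applied literally and the cesarean share is 10% to 30%. That share is an assumption, as are proportional hazards, the carried-over 50% and 30% rates, and cesarean being unrelated to redosing. If the sentence was meant only for women not yet redosed, no events are lost and only the wording is at fault. No size can be put on the group with a request but no bolus. Nothing here calls the primary comparison or the 106 per group into question.

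**What to change.** Before unblinding:

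1. Keep the proportion needing a manual bolus as primary. Reword Aim 1 and its hypothesis, in sections 1.0 and 2.0, to match the section 3.0 hypothesis that women assigned to 300 mL/h are less likely to need a manual bolus.
2. List time to first redose among the secondary outcomes in sections 3.0 and 5.0, and state that any claim about duration rests on it.
3. Use one event definition in the aim, outcomes, data sheet and analysis. Manual bolus given needs the fewest edits, because the primary outcome, its planning rates and the section 5.0 time endpoint already use it.
4. Replace the censoring sentence with: a woman with the event counts at the time of that event whatever her mode of delivery, and every woman without it is censored at delivery.

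This is a change of wording only. Both times are already collected and the log-rank test is already planned, so no patients, data or tests are added. The price is that the duration claim becomes explicitly secondary.

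### Women are excluded for catheter replacement during labor, which can follow study boluses and the primary endpoint itself, and no analysis population keeps them

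*Combined protocol and SAP*

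**What the plan says.** Section 3.0, under Size of study groups, defines the primary outcome as the proportion of women who "have breakthrough pain requiring a manual bolus (redose) by the anesthesiologist". Section 5.0, Data evaluation, repeats it: "The primary outcome will be the proportion of patients requiring supplemental manual boluses of local anesthetic".

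The exclusion criteria in section 3.0 (.2.1) cover failed combined spinal-epidural (CSE) analgesia and also women who "need to have the epidural catheter replaced during labor, or who deliver within 90 minutes of initiation of labor analgesia will be excluded". The last two criteria cannot be applied at screening, because they depend on what happens during labor. The sample-size text confirms that losses after enrolment are meant: it refers to "enrolled patients being excluded from this study for both clinical and personal reasons" and recruits 300 so that 106 per group remain.

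On timing, section 3.0 (.2.2) states: "The first bolus will be given 30 minutes after intrathecal injection". Timed boluses then follow every 60 minutes. The patient, the anesthesiologist and the nurse recording data are blinded. Breakthrough pain is assessed and then managed as usual, and nothing in the text prevents a replacement after a redose.

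Section 5.0 names the tests and a censoring rule for the time outcomes. It does not define an analysis population or say how a woman with a replaced catheter counts in the primary proportion.

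**The concern.** The rule selects women on something that happens after randomised treatment has begun. A woman who is redosed and later has her catheter replaced has had the primary event, yet she leaves both numerator and denominator. If bolus rate changes how often catheters are replaced, the two arms lose different numbers of such women, and the remaining groups are no longer protected by randomisation.

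Replacement is plausibly linked to inadequate analgesia, but that is inference. The plan gives no reasons for replacement, and a catheter can fail for purely technical causes.

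Exclusion for delivery within 90 minutes has the same form but matters less. If the 90 minutes run from the intrathecal dose, these women receive at most one full timed bolus, so an effect of bolus rate on this exclusion is less likely.

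**Working it through.** **Inputs from the plan.** Redose rates 50% (100 mL/h) and 30% (300 mL/h), power 0.8, alpha 0.05, 106 per group, 300 recruited. Two-sided testing is assumed, because sidedness is stated only for the t-test.

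**Reproducing the plan's figure.** The two-proportion formula gives 93 per group without continuity correction and 103 with it, within 3% of 106. Fisher's exact test at 106 has power 0.816. The sample size is not in dispute. The implied loss is 1 − 212/300 = 29.3%.

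**Assumed inputs.** The plan gives neither replacement rates nor the time of randomisation. I assume 150 randomised per arm (300/2). Let p be the true event rate, c the fraction removed, and f the share of removed women who had already met the endpoint.

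**Formula.** Observed rate = (p − f·c)/(1 − c). There is no shift if f = p. Power uses pooled null variance, two-sided 0.05, with n = 150(1 − c) per arm.

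**True effect, 50% v 30%.** Example for 8% v 2% removed at f = 1: (0.50 − 0.08)/0.92 = 45.7% and (0.30 − 0.02)/0.98 = 28.6%, a difference of 17.1 points.

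| Removed, 100 v 300 mL/h | f | Difference (points) | Power |
|---|---|---|---|
| none | – | 20.0 | 0.95 |
| 8% v 2% | 1 | 17.1 | 0.85 |
| 8% v 2% | 0.7 | 19.1 | 0.91 |
| 8% v 2% | 0.5 | 20.4 | 0.94 |
| 2% v 1% | 1 | 19.7 | 0.94 |
| 2% v 8% | 1 | 25.1 | 0.99 |
| 2% v 8% | 0.5 | 21.7 | 0.97 |

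If only 106 per group are left for analysis, the 8% v 2% case has power 0.73 (f = 1), 0.82 (f = 0.7) or 0.86 (f = 0.5), against 0.85 undistorted.

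**No true effect, 40% in both arms.** This is a special case: bolus rate changes replacement while the total redose rate stays equal.

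| Removed, 100 v 300 mL/h | f | Type I error |
|---|---|---|
| 5% v 5% | 1 | 5.0% |
| 2% v 1% | 1 | 5.1% |
| 4% v 2% | 1 | 5.6% |
| 8% v 3% | 0.5 | 5.1% |
| 8% v 3% | 0.7 | 6.0% |
| 8% v 3% | 1 | 9.0% |

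In the last row, 8.5 of the 9.0 percentage points are false findings in favour of 100 mL/h and 0.5 in favour of 300 mL/h. Reversing the imbalance reverses that split. Simulation of 400,000 trials per case gave 9.1%, 6.0% and 5.2% for 8% v 3% at f = 1, 0.7 and 0.5, and 5.1% for 5% v 5%.

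**Early delivery.** Removing 5% non-events per arm gives 0.50/0.95 = 52.6% and 0.30/0.95 = 31.6%, a difference of 21.1 points.

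**What a literal all-randomised set could cost.** If randomisation precedes the CSE, some randomised women receive no study bolus. As an upper bound, suppose all 44 of 150 lost per arm have the same event rate in both arms. The difference becomes 20 × 106/150 = 14.1 points. Power at 150 per arm is then 0.78 if that common rate is 0% and 0.70 if it is 50%.

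**The case against.** The strongest reply is that every ingredient of the harm is assumed: the replacement rate, the imbalance between arms, and the share already redosed. That stands. The larger figures need a marked imbalance with nearly all replaced women already redosed, and milder inputs leave almost nothing.

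Blinding is a real safeguard. The replacement decision is made without knowledge of the arm, so the only route left is an effect of bolus rate on the need for replacement. Blinding does not close that route.

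A reader might infer a direction from the Background, which reports that "dye injected at high pressures had more uniform spread through the epidural space", and conclude that the slower rate would lead to more replacement. The documents do not support that step. The observation concerns dye spread in cadavers and is offered in support of intermittent injection, which both arms receive. It says nothing about catheter failure. A reader might also infer that the rule favours the trial's hypothesis. That would need more replacement of already redosed women at 300 mL/h, and nothing in the plan suggests it. The opposite imbalance would shrink the benefit.

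A fair objection to the remedy is that analysing literally every randomised woman could bring in failed CSEs and dilute the comparison below the planned power. That also stands, and it is why the population proposed below starts when the pump programme starts.

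**Conclusion.** The gap is real and should be fixed. The plan states a rule that can delete women after they have met the primary endpoint, and it names no analysis that keeps them. This rests on the text alone.

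The size and direction of any bias are unknown, and the bias may be negligible. It requires replacement to depend on bolus rate. Under no true effect, equal removal with the same share already redosed leaves type I error at 5%. The 9.0% type I error and the 0.73 power are illustrations under strong assumptions. It would be wrong to read them as estimates for this trial, or to conclude that its result will be biased. The practical point is that, without exclusions reported by arm or an analysis that keeps these women, a reader of the result could not tell whether the rule mattered.

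**What to change.** 1. Make the primary population all randomised women in whom the assigned pump programme was started, analysed in their assigned arm. State the time of randomisation. Failed CSE and other losses before that start may stay excluded, because the assigned rate cannot have affected them, provided they are reported by arm.
2. Count a manual redose through the original catheter as an event even if replacement follows. State in advance whether manual doses through a replacement catheter count; I suggest not in the primary analysis.
3. Count women who deliver within 90 minutes without a redose as non-events.
4. Add two sensitivity analyses: one counting replacement for inadequate analgesia as an event, since a woman replaced without a redose is otherwise a non-event; the other using the present exclusion set.
5. State that recording on the study data sheet continues for these women, and that the step by which "pump utilization data will be downloaded from epidural pumps after delivery" applies to them too. The plan gives no stopping point for either, but does not say that they continue after exclusion.
6. Record the reason for each replacement, and report exclusions by arm with reasons.

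The cost is protocol and analysis wording, one extra data field and continued recording for women now excluded. Clinical care does not change. The downside is slight dilution from women who received few study boluses. Starting the population at the pump programme keeps out women who never reached study treatment, so the upper-bound dilution shown above should not arise.

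### PCEA requests and deliveries are analysed as raw totals although time under analgesia varies; adding a per-hour or offset analysis is a cheap, optional gain, with most new information for requests

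*Combined protocol and SAP*

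**What the plan says.** Section 3.0 .2 (Methods) and section 5.0 .2 (Data evaluation) carry the same sentence: "Secondary outcomes are the total number of requested and delivered PCEA boluses, and bupivacaine consumption per hour of labor analgesia". The comma attaches the hourly scale most naturally to bupivacaine alone. Section .2.2 lists the pump download as counts and an amount: "the number of PCEA demands, the number of times that PCEA boluses were delivered, the total amount of local anesthetic consumed". For continuous data section 5.0 .2 names a two-tailed t-test or a Mann-Whitney U test, with no offset or adjustment for duration.

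Time under analgesia will differ between women. Section .2.1 admits nulliparous women, induced or in spontaneous labor, who "request neuraxial labor analgesia at < or = to 5cm cervical dilation are eligible to participate". The only stated bound on exposure is the exclusion of women "who deliver within 90 minutes of initiation of labor analgesia will be excluded from the study".

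Dosing apart from bolus rate is common to both arms: "The intermittent bolus volume will be 10 mL administered every 60 minutes", plus PCEA "boluses of 5 mL every 10 minutes to a maximum of 15 mL (three PCEA boluses in a one hour period".

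Section 5.0 .2 also plans time to first PCEA request, compared by Kaplan-Meier and log-rank methods.

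**The concern.** A woman under analgesia for twelve hours can press the button more often than one who delivers after three, whatever the bolus rate does for her pain. The plan allows for this in bupivacaine but not in the two counts named in the same sentence. Where duration varies widely, that variation enters the totals as noise, and a real difference in hourly PCEA demand becomes harder to detect.

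What is at stake is precision on two secondary outcomes. Duration is also observed after randomization, so its balance is an assumption. If bolus rate affected duration, totals and hourly rates would answer different questions.

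**Working it through.** **The plan's own figure.** The only sample size stated is for the primary outcome, 50% against 30%. Two-sided 0.05, power 0.80:

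- n = [1.96 √(2 × 0.4 × 0.6) + 0.8416 √(0.25 + 0.21)]² / 0.2² = 93 per group.
- With continuity correction: (93/4) × [1 + √(1 + 4/(93 × 0.2))]² = 103.

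The stated 106 is within 3% of this, and the present point does not touch it. The plan states no effect size, SD or power for the PCEA outcomes.

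**Why totals add variance.** Expected total = hourly rate × hours. On the log scale, leaving out counting noise,

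Var(log total) = σ_R² + σ_T² + 2ρσ_Rσ_T,

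where ρ is the correlation of log rate with log duration. The total is the less variable measure only if ρ < -σ_T/(2σ_R). With an assumed between-woman CV of 0.5, σ_R = √ln(1.25) = 0.472. The break-even ρ is then about -0.21, -0.42 and -0.64 for σ_T = 0.2, 0.4 and 0.6.

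**Simulated size.** The documents give no durations or PCEA rates, so these inputs are assumed: 106 per arm (from the plan), median 6 h, log-normal duration with labors under 1.5 h excluded, 1.2 requests per hour, rate CV 0.5, 20% lower rate in one arm, deliveries capped at three per hour. Two-sided Mann-Whitney at 0.05, 2000 trials per setting. Power, total against per hour:

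| Outcome, ρ | σ_T 0.2 | σ_T 0.4 | σ_T 0.6 |
|---|---|---|---|
| Requests, +0.3 | 0.57 v 0.67 | 0.47 v 0.67 | 0.35 v 0.64 |
| Requests, 0 | 0.64 v 0.67 | 0.53 v 0.65 | 0.43 v 0.65 |
| Requests, -0.3 | 0.69 v 0.66 | 0.64 v 0.67 | 0.51 v 0.65 |
| Requests, -0.5 | 0.73 v 0.67 | 0.72 v 0.67 | 0.61 v 0.65 |
| Deliveries, +0.3 | 0.560 v 0.661 | 0.442 v 0.666 | 0.318 v 0.636 |
| Deliveries, 0 | 0.628 v 0.668 | 0.504 v 0.640 | 0.402 v 0.645 |
| Deliveries, -0.5 | 0.713 v 0.657 | 0.700 v 0.669 | 0.573 v 0.638 |

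The crossings fall where the break-even formula puts them. Type I error with balanced duration is 4-6% for every measure.

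**Stronger negative dependence.** For requests at ρ = -0.7, power is 0.78 / 0.79 / 0.71 on totals against 0.68 / 0.68 / 0.67 per hour, a gain for totals of 10, 11 and 4 points. Another simulation at ρ = -0.7 gave 8-12. At ρ = -0.8 it is 0.79 / 0.84 / 0.80 against 0.66 / 0.65 / 0.67, a gain of 13, 19 and 13 points.

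**A different model.** This one simulates the 10-minute lockout and hourly maximum, with mean duration 5-9 h, duration CV 0.3-0.7, 1 or 2.5 requests per hour, rate CV 0.6 or 1.2, and a 25% lower rate. Relative efficiency above 1 favors per hour.

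- Rate unrelated to duration (36 scenarios): 1.01-3.17 for requests, 1.06-5.19 for deliveries. The figure for deliveries was the higher in 34 of the 36.
- Rate falling as 1/duration (7 h only): 0.39-0.87 for requests, 0.65-0.98 for deliveries, so totals win.

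**What bupivacaine per hour already covers.** At 0.625 mg/mL, a programmed bolus is 10 × 0.625 = 6.25 mg and a delivered PCEA bolus is 5 × 0.625 = 3.125 mg. Pump bupivacaine per hour is therefore roughly 6.25 + 3.125 × (deliveries per hour). Across the two models it correlates 0.93-0.997 with deliveries per hour, manual redoses omitted. Refused presses add no drug: its correlation with requests per hour is 0.86-0.97 with an hourly cap only, and 0.80-0.93 when the lockout is simulated.

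**Unequal duration.** With equal hourly rates and 20% shorter duration in one arm, a t-test on totals rejected in about 46% of simulated trials, against about 4% per hour.

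**The case against.** The strongest reply is that nothing here is an error. Cumulative demand is a legitimate outcome, the tests on it hold their level when duration is balanced, and the plan sets no power target for secondary outcomes. That stands, and it is why the point is optional. It is also possible to read the hourly scale as covering all three items. If that was meant, one clarifying sentence is still worth having.

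Requests are not left wholly uncovered. Time to first PCEA request allows for unequal follow-up, but it sees only the first press and so covers request behaviour only in part.

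An advantage for the hourly scale cannot be proved from the documents. They hold no data on how hourly use varies with labor length, and under strong negative dependence totals are clearly better.

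Stronger readings are tempting and should be resisted:

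- A reader might infer that totals produce false positives. With balanced duration they do not. With unequal duration, the 46% above reflects a real difference in total use, which is a different question.
- A reader might infer that the precision loss falls mainly on requests. The figures show at least as large a loss for deliveries; only the added information is mainly for requests.
- A reader might infer that totals should be dropped. If durations differed by arm, both scales would be needed.

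**Conclusion.** A cheap, optional improvement. The plan leaves two of its three named secondary outcomes unadjusted for time under analgesia while adjusting the third. In the main settings the effect of using totals for requests runs from a 29-point loss of power (ρ = +0.3, σ_T = 0.6) to a 6-point gain (ρ = -0.5, σ_T = 0.2). For deliveries it runs from a 32-point loss to a 6-point gain. The 6 points are not an upper limit: they reflect where that range of correlations stops, and totals gain more beyond it.

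That totals usually lose precision rests on hourly use not falling clearly with longer labor, which the documents can neither confirm nor exclude. All durations, request rates and effect sizes are assumptions. The primary outcome, the 106 per group and the type I error are unaffected.

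**What to change.** In sections 3.0 .2 and 5.0 .2, state that PCEA requests and deliveries will be analysed per hour of labor analgesia, using the same denominator as bupivacaine, preferably by a negative binomial model with log hours as offset. Keep reporting the totals alongside. If only one count is changed, it should be requests.

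The cost is one sentence in each section and no new data: the counts are in the pump download, and bupivacaine per hour already needs the hours.

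There are two downsides. Rates are noisier in short labors: simulated SD of requests per hour 0.92 at 1.5-3 h against 0.71 at 6-12 h, and for deliveries 0.78 against 0.59. A simple per-hour comparison can also have less power than totals if hourly use falls strongly with duration, by about 6 points at correlation -0.5 and more beyond. The offset model reduces both. For requests, with correlations of -0.5, 0 and +0.3 and σ_T of 0.2 and 0.6, it had power 0.69-0.77 and type I error 3-6% (400 trials each). It was not tried at stronger negative dependence.
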